STUDY PROTOCOL

The Effect of Menstrual Cycle on the Results of Treadmill Exercise Test with High Sensitive Cardiac Troponin Levels after Exercise in Women

Name of Study:

The Effect of Menstrual Cycle on the Results of Treadmill Exercise Test with High Sensitive Cardiac Troponin Levels after Exercise in Women

Study Design:

Observational Study Model: Case-Crossover

Time Perspective: Prospective

Biospecimen Retention: None Retained

Study coordinator and principal investigator:

Investigator: [name] MD [[name]]

Official Title: Medical Doctor, Professor of Cardiology

Affiliation: Istanbul Medeniyet University, Istanbul Turkey

Istanbul, Istanbul, Turkey

Co-investigators

[name], Affiliation: Istanbul Medeniyet University, Istanbul Turkey

Istanbul, Istanbul, Turkey

Supported by: Istanbul Medeniyet University

1. OBJECTIVE AND HYPOTHESES

Objective: To compare exercise treadmill test (ETT) results in premenopausal women at the early and late follicular phases of the menstrual cycle.

General Hypothesis:

False positive results are commonly observed in women after exercise treadmill test (ETT). The studies report severe variability in the sensitivity and specificity of ETT in detecting significant coronary artery disease (CAD). Sensitivity ranges from 23% to 100% and specificity ranges from 17% to 100% (1, 2). ETT utilizes electrocardiography (ECG) along with heart rate (HR) and blood pressure (BP) monitoring during exercise, typically involving a treadmill. The major finding of ETT is the ST segment deviation from the baseline. False positive stress ECGs are common especially in premenopausal women, limiting the specificity of the test (3-6).

Menstrual periods can cause biological variability in ETT in premenopausal women (7). The menstrual period is divided into phases: early follicular (days 1-5), late follicular (days 6-12), ovulation (days 13-15), early luteal (days 16-19), mid-luteal (days 20-23) and late luteal phases (24-28 days). Early follicular phase is characterized by low estrogen and low progesterone, late follicular phase is characterized by low progesterone and high estrogen. Mid-luteal phase is characterized by high progesterone and high estrogen levels (7-9). Early and late follicular phases of the menstrual cycle in women demonstrate nearly 4 fold differences in estrogen levels. The menstrual period phase affects thermoregulation and physical working capacity in women (9, 10). Estrogen has protective and vasodilatory effects on the cardiovascular system (11). With the discovery of high sensitive cardiac troponins (hs-cTn), minute changes of hs-cTn have become detectable (12).

The effects of menstrual periodic changes on the results of exercise treadmill test in premenopausal women have not been clearly defined. Primary purpose of the study is to investigate the biological causes of false positive test results in the treadmill exercise test in premenopausal women. Estrogen is known to have direct vasodilatory effects on coronary arteries. Early and late follicular phases of the menstrual cycle are characterized by low and high estrogen levels, respectively. The Early Follicular Phase starts on the first day of the menstrual cycle and ends when oestradiol begins to increase. It is characterised by increasing LH and FSH and constant low levels of oestradiol. The late follicular phase starts with the increase in oestradiol and ends at its preovulatory peak (7-10). False positive stress ECGs are commonly reported especially in premenopausal women, limiting the specificity of the ETT (3-5). Studies demonstrated that HR adjustment of in exercise-induced ST segment depression using the ST/HR slope or ST/HR index could improve the sensitivity and specificity of ETT (2, 13-15).

The hypothesis of the study is that ETT results and hs-cTnT release after ETT will change at the early and late follicular phases in premenstrual women.

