2. STUDY ENDPOINTS

The major finding of ETT is the ST segment deviation from the baseline. The ST segments are evaluated 60-80 ms after the J point. ECG positive ETT result was defined as ≥ 1 mm (0.1 mV) horizontal or downsloping ST depression in at least 3 consecutive beats.

Chest pain or inadequate hemodynamic response during ETTs are considered clinically positive ETT result. Tests that do not meet these criteria but show ST segment changes or had low diagnostic value due to baseline ECG changes are considered indeterminate ETT results.

Automated measurements and mathematical calculations are recorded in the ETT system (General Electronic GE Healthcare T2100-ST Treadmill & CASE 6.73 Stress Test System).

ETT results are evaluated by 2 different cardiologists and categorized as positive/indeterminate/negative ETT results.

Hs-cTn is measured before and 15 minutes after ETT.

Indices of ST/HR slope and the ST/HR index were reported automatically by the General Electronic GE Healthcare T2100-ST Treadmill & CASE 6.73 Stress Test System device. The primary endpoint in the study was the ST/HR index. The secondary endpoints were ST/HR slope, maximum ST segment depression (mm), HR and BP response to exercise, maximum exercise capacity, and the change in hormones and hs-cTn after ETT.

Primary endpoint:

ST/HR index during ETTs at the early and late follicular phases of the menstrual cycle

(μ V/beat per minute (bpm))

Secondary endpoints:

1. Change in maximal exercise capacity with exercise and menstrual cycle (METs score)
2. Maximum ST segment depression (mm)
3. ST/HR slope (μ V/beat per minute (bpm))
4. The change in high-sensitive cardiac troponin T after ETT (ng/L)
5. Hormone levels (estrogen) at the early and late follicular phases of the menstrual cycle

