The early and late follicular phases are determined from the history. The early follicular phase ETT is planned on the 3rd day of menstrual bleeding, while the menstrual bleeding continues. The late follicular phase ETT is planned on the 3rd day after the menstrual bleeding ends. Hormone levels are measured before each ETT to ascertain the phase of the menstrual cycle. Two ETTs are performed on each participant.

The blood sample is taken 30 minutes before the ETT to measure follicular stimulating hormone (FSH), luteinizing hormone (LH), estrogen, progesterone, and hs-cTn. After the test, the patient is allowed to rest for 15 minutes and blood is taken to check the 2nd hs-cTn after ETT.

Sampling Method: Probability Sample

Minimum Age: 20 years

Maximum Age: 55 years

Sex: Female

Gender Based: Yes

Female patients in the pre-menopausal period

The inclusion criteria are:

1. Premenopausal female patients with regular menstrual cycles,
2. ages between 20-55,
3. Patients have been seen in the cardiology clinic by a cardiologist for the symptoms of chest pain with a clinical suspicion of angina or angina equivalent.
4. A cardiologist has ordered ETT as a diagnostic test for the symptoms of chest independent of the study protocol
5. Patients can understand and sign the informed consent.

[figure not shown]
The exclusion criteria are:

1. Women with menopause or menopause-related symptoms or menstrual cycle irregularity or use of hormonal therapy or oral contraceptives, current pregnancy
2. patients with a history of CAD,
3. secondary or uncontrolled hypertension,
4. history of valvular heart disease,
5. left ventricular hypertrophy on echocardiography,
6. abnormal systolic or diastolic function or wall motion abnormality on echocardiography,
7. history of cardiac arrhythmia or heart failure, pericarditis or myocarditis
8. history of cancer, stage ≥ 3 kidney failure, liver failure, history of psychiatric illness, history of, recent infection.
9. pre-existing ECG abnormality that would confound the interpretation during the ETT (baseline ECG was considered abnormal in the presence of the following findings: prolonged QT interval, chamber hypertrophy, alterations in the ST-T waves, any degree of heart block, T-wave abnormalities, premature ventricular contractions (PVCs), right bundle branch block (RBBB), left bundle branch block (LBBB), left or right axis deviation, or any abnormal rhythm other than normal sinus rhythm).

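### The protocol states its primary purpose as explaining false positive ETT results, but no positive ETT can be identified as false, and the recorded ETT classification has no endpoint status and no paired analysis

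*Protocol*

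**What the plan says.** **Purpose and objective.** Protocol section 1 gives two aims of different reach. The formal one is "Objective: To compare exercise treadmill test (ETT) results in premenopausal women at the early and late follicular phases of the menstrual cycle". Later in the same section comes a broader one: "Primary purpose of the study is to investigate the biological causes of false positive test results". The hypothesis follows the narrower aim: "The hypothesis of the study is that ETT results and hs-cTnT release after ETT will change at the early and late follicular phases". The SAP's null hypothesis is narrower again and concerns only the ST/HR index.

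**Population and coronary status.** Inclusion criterion 3 in Protocol section 3 reads in part "Patients have been seen in the cardiology clinic by a cardiologist for the symptoms of chest pain with a clinical suspicion of angina". The exclusions cover a history of CAD, abnormal function or wall motion on echocardiography, left ventricular hypertrophy, heart failure, and a baseline ECG that would confound the reading. The schedule in section 4 has two ETTs with blood tests and day-7 phone visits. It contains no coronary imaging, stress imaging or diagnostic follow-up.

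**Endpoints.** In Protocol section 2, "The primary endpoint in the study was the ST/HR index", a continuous measure for which no positivity cut-off is given. The same section defines an ECG-positive ETT (at least 1 mm of horizontal or downsloping ST depression in three or more consecutive beats). It then adds "Chest pain or inadequate hemodynamic response during ETTs are considered clinically positive ETT result". Two cardiologists read each test, and the results are "categorized as positive/indeterminate/negative ETT results". The secondary list begins "The secondary endpoints were ST/HR slope, maximum ST segment depression (mm), HR and BP response to exercise, maximum exercise capacity" and goes on to hormones and troponin. Neither the Protocol list nor the SAP list contains the ETT classification.

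**Analysis.** Under its statistical tests, the SAP gives a paired t-test or Wilcoxon test for numerical data and a chi-square test between groups for categorical data. It names no categorical variable.

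**The concern.** A false positive is a positive test in a woman without the disease. Protocol section 1 itself frames ETT accuracy as detection of significant CAD. Excluding known CAD and abnormal resting findings makes undiagnosed disease less likely but does not settle it, because suspected angina is the reason these women are tested. Nothing in the text says how a positive result would be judged false.

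What is at stake is the conclusion. A phase difference in ST/HR index is a finding about the ETT. Under the stated primary purpose, it could be presented as a biological cause of false positives, which the data cannot show.

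There is a second gap. The variable closest to the stated purpose is whether a test was read as positive. It is collected but has no endpoint status. If it were analysed with the one categorical test the SAP offers, the two results from each woman would be treated as if they came from different women.

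**Working it through.** **1. The plan's own sample size.** Inputs from the SAP: effect size 0.5, type I error 5% two-sided, power 80%, paired sample. For a paired t-test the noncentrality is 0.5 × √34 = 2.915 on 33 degrees of freedom, giving power 0.808. N = 33 gives 0.795. The stated 34 is reproduced. It sizes the ST/HR index comparison and no comparison of positive results.

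**2. Can a positive be called false?** For each item that bears on coronary status:

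| Item | What it establishes |
|---|---|
| No history of CAD | No known disease |
| Normal resting echocardiogram | No resting dysfunction or wall motion abnormality |
| Normal baseline ECG | A readable tracing |
| hs-cTn before and after ETT | A secondary endpoint, not used to classify an ETT as true or false |
| Day-7 phone visits | No diagnostic work-up listed |

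None of these separates a true from a false positive in a woman with suspected angina.

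**3. How wide the uncertainty is.** False share of positives = (1 − prev)(1 − spec) / [prev × sens + (1 − prev)(1 − spec)]. Sensitivity (23% to 100%) and specificity (17% to 100%) are the ranges in Protocol section 1. The documents give no prevalence, so 2% to 20% is an assumption.

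- Specificity 100%: the numerator is 0, so the false share is 0%.
- Prevalence 2%, sensitivity 23%, specificity 17%: 0.98 × 0.83 = 0.8134; 0.02 × 0.23 = 0.0046; 0.8134 / 0.8180 = 99.4%.
- Prevalence 10%, sensitivity 100%, specificity 17%: 0.90 × 0.83 = 0.747; 0.747 / 0.847 = 88.2%.
- Prevalence 20%, sensitivity 23%, specificity 17%: 0.80 × 0.83 = 0.664; 0.664 / 0.710 = 93.5%.

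The study's data cannot place it within 0% to 99.4%.

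**4. What a paired analysis of ECG-positive ETT could do at N = 34.** Only discordant women (positive in one phase, not in the other) carry information on a phase difference. The discordance rates are assumptions, and the test is exact two-sided McNemar at 5%.

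| Positive in one phase only vs the other only | Expected discordant women | Power at 34 | N for 80% power |
|---|---|---|---|
| 10% vs 2% | 34 × 0.12 = 4.1 | 7% | 153 |
| 20% vs 5% | 34 × 0.25 = 8.5 | 29% | 92 |
| 30% vs 5% | 34 × 0.35 = 11.9 | 65% | 45 |

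Five discordant women all in one direction give p = 2 × 0.5⁵ = 0.0625, and six give 2 × 0.5⁶ = 0.031. Fewer than six discordant women can never reach significance.

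**The case against.** The strongest reply is that the narrower aim is already in the documents. The formal objective, the hypothesis and the SAP null hypothesis all concern phase differences, and neither document plans a false positive rate or a specificity estimate. On that view this is one over-broad sentence among background text. Much of this stands: the primary analysis needs no reference standard. But the sentence is labelled the primary purpose, and it conflicts with the objective in the same section.

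A second reply is that each woman is her own control. If her coronary status is the same at both tests, a woman who is positive in one phase and negative in the other has one wrong result. That is real partial information. It does not show whether the positive or the negative was wrong. One woman's change may also be test-retest variation, so phase dependence needs an asymmetry across the group. No such analysis is planned.

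A third reply is that maximum ST depression is already a secondary endpoint and ECG positivity is largely that variable cut at 1 mm. The overlap is real and limits what the binary endpoint adds. The classification is nonetheless the variable closest to the stated purpose.

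A reader might infer that the positive category is contaminated by the complaint on which women were enrolled. The documents do not support going that far. Section 2 counts chest pain during the ETT, whereas enrolment rests on earlier symptoms, and ECG-positive and clinically positive are defined separately. Merging them into one category is a plausible reading of the three-level wording, but it is not stated.

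**Conclusion.** The point holds for the stated primary purpose: no positive ETT can be identified as false, so no conclusion about the cause or rate of false positives is supported. A reader might infer that the study can say nothing relevant to false positives, or that it fails as a whole. Neither follows. The phase comparison of ETT results and the ST/HR index comparison remain answerable, and discordant results carry partial information.

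The 0% to 99.4% range rests on an assumed prevalence and combines the extremes of two separately reported ranges. It shows that the false share is not identified; it does not measure bias in any planned endpoint. The power figures of about 7% to 65% rest on assumed discordance rates.

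The missing endpoint status follows directly from the two lists. The chi-square problem arises if that test is used to compare the ETT classification between phases; the SAP offers no other categorical test. The study flow figure is not available here, so a work-up drawn only there cannot be excluded, but nothing in the text or schedule points to one.

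**What to change.** 1. In Protocol section 1, reword the primary purpose and the permitted conclusion as phase-dependent change in ETT findings in premenopausal women without known CAD. Make no claim about the cause or rate of false positives.
2. In both endpoint lists, add ECG-positive ETT as a secondary endpoint, using the protocol's existing 1 mm rule. Report it separately from clinically positive ETT.
3. In the SAP's statistical tests, replace the chi-square for this between-phase comparison with exact McNemar, and report the paired difference in proportions with its confidence interval.

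The cost is one reworded purpose statement, one line in each endpoint list and one sentence in the SAP. No procedure, visit or change of sample size is needed. The downsides are a less ambitious claim and a binary endpoint that partly overlaps maximum ST depression and has low power at 34 women. It should be presented as estimation, not as a confirmatory test.

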2. STUDY ENDPOINTS

The major finding of ETT is the ST segment deviation from the baseline. The ST segments are evaluated 60-80 ms after the J point. ECG positive ETT result was defined as ≥ 1 mm (0.1 mV) horizontal or downsloping ST depression in at least 3 consecutive beats.

Chest pain or inadequate hemodynamic response during ETTs are considered clinically positive ETT result. Tests that do not meet these criteria but show ST segment changes or had low diagnostic value due to baseline ECG changes are considered indeterminate ETT results.

Automated measurements and mathematical calculations are recorded in the ETT system (General Electronic GE Healthcare T2100-ST Treadmill & CASE 6.73 Stress Test System).

ETT results are evaluated by 2 different cardiologists and categorized as positive/indeterminate/negative ETT results.

Hs-cTn is measured before and 15 minutes after ETT.

Indices of ST/HR slope and the ST/HR index were reported automatically by the General Electronic GE Healthcare T2100-ST Treadmill & CASE 6.73 Stress Test System device. The primary endpoint in the study was the ST/HR index. The secondary endpoints were ST/HR slope, maximum ST segment depression (mm), HR and BP response to exercise, maximum exercise capacity, and the change in hormones and hs-cTn after ETT.

Primary endpoint:

ST/HR index during ETTs at the early and late follicular phases of the menstrual cycle

(μ V/beat per minute (bpm))

Secondary endpoints:

1. Change in maximal exercise capacity with exercise and menstrual cycle (METs score)
2. Maximum ST segment depression (mm)
3. ST/HR slope (μ V/beat per minute (bpm))
4. The change in high-sensitive cardiac troponin T after ETT (ng/L)
5. Hormone levels (estrogen) at the early and late follicular phases of the menstrual cycle

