3. STUDY DESIGN

The study is performed in the cardiology clinics of a tertiary care training hospital. The study is approved by the local ethics committee (number 2023/0129 on 22/02/2023).

Study Population:

The study population consists of premenopausal women who applied to the outpatient clinic with chest pain between February 2023 and July 2023. Patients report that they have a regular menstrual cycle.

Written informed consent is obtained from the patients.

All patients have transthoracic echocardiography. Echocardiography demonstrates normal left ventricular systolic and diastolic function. Echocardiography does not show wall motion abnormality or significant valvular heart disease.

All patients are evaluated for cardiovascular risk. Risk factors such as hypertension, diabetes mellitus, cigarette smoking, hyperlipidemia, family history of CAD, and drug use are questioned (16). Cardiovascular risk factors are defined as follows. Hypertension is defined as a persistent elevation in office systolic BP ≥ 140 and/or diastolic BP ≥ 90 mmHg, or a 24-hr ambulatory BP monitor average of $\geq 130/80$, or requirement of chronic use of antihypertensives. Hyperlipidemia is defined as elevated total cholesterol (>240 mg/dl), low-density lipoprotein cholesterol (LDL-C) (>160 mg /dl), triglycerides > 150 mg/dl, high-density lipoprotein cholesterol (HDL-C) (< 50 mg /dl). Cigarette smoker is defined as having smoked at least 100 cigarettes in lifetime. Type 2 diabetes mellitus is defined as fasting plasma glucose (FPG) ≥ 126 mg/dL, or 2-hour plasma glucose ≥ 200 mg/dL during a 75-g oral glucose tolerance test (OGTT), or random plasma glucose ≥ 200 mg/dL in a patient with classic symptoms of hyperglycemia, or hemoglobin A1c (HbA1c) $\geq 6.5\%$ (48 mmol/mol). Self-reported family history of premature CAD is defined as having a first-degree relative with premature CAD (men, age <55 years; women, age <65 years).

Menstrual cycle

The history of the menstrual cycle of the patient is obtained in detail. The duration and regularity of the menstrual cycle, the amount of bleeding, and the number of days the bleeding lasted are noted for each patient. Patients with irregular menstrual cycles, breakthrough bleeding, spotting, gynecological examination, or treatment plan that would disrupt the menstrual cycle are excluded from the study.

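### The single positive ETT level appears to combine ECG-positive with symptom- or haemodynamic-positive tests, and no analysis of ECG positivity alone is planned

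*Protocol*

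**What the plan says.** Protocol section 2 (Study Endpoints) gives two routes to a positive test.

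- ECG route: "ECG positive ETT result was defined as ≥ 1 mm (0.1 mV) horizontal or downsloping ST depression in at least 3 consecutive beats".
- Clinical route, with no ST requirement: "Chest pain or inadequate hemodynamic response during ETTs are considered clinically positive ETT result".

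The indeterminate level is what remains after both: "Tests that do not meet these criteria but show ST segment changes", together with tests of low diagnostic value because of the baseline ECG. Two cardiologists then assess the tests, which are "categorized as positive/indeterminate/negative ETT results".

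Protocol section 1 sets the objective: "To compare exercise treadmill test (ETT) results in premenopausal women at the early and late follicular phases of the menstrual cycle". The hypothesis is likewise about ETT results (and troponin release). The same section motivates the study by the stress ECG: "False positive stress ECGs are commonly reported especially in premenopausal women, limiting the specificity of the ETT".

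Protocol section 3 (Study Design) describes the population as "premenopausal women who applied to the outpatient clinic with chest pain", and the third inclusion criterion requires referral "for the symptoms of chest pain with a clinical suspicion of angina or angina equivalent". The early test is planned during menstrual bleeding and the late test after it has ended.

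The three-level category is in neither list of endpoints (protocol section 2; SAP, primary and secondary endpoints). The SAP's only provision for such data is a general sentence assigning the chi-square test to categorical comparisons.

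**The concern.** There is one positive level, and indeterminate is the remainder after both definitions. A test with chest pain but no qualifying ST depression therefore has nowhere to go except positive. It would count the same as a test with ST depression of 1 mm or more.

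The study's question concerns positive stress ECGs, and its proposed mechanism, an oestrogen effect on the coronary arteries, is looked for in the ST segment. Chest pain on the treadmill may simply repeat the symptom that brought the woman to clinic. It is self-reported by someone who knows whether she is bleeding. Pooling then does two things:

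- An ECG change between phases is invisible in a woman who is clinically positive at both tests.
- A change in pain alone produces a discordant pair that has nothing to do with the ST segment.

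At stake is the categorical answer to the stated objective. A reader who wants to know how many women switch between ECG-positive and ECG-negative could not get that from the pooled level. The continuous ST endpoints do not report it either.

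**Working it through.** **1. The plan's own figure.** The SAP gives 34 patients for a paired comparison with effect size 0.5, type I error 5% and power 80%. For a two-sided paired t-test, power comes from the noncentral t distribution with n − 1 degrees of freedom and noncentrality 0.5·√n. At n = 34 this gives 0.808, and 34 is the smallest n that reaches 0.80. The figure reproduces. It is sized on the ST/HR index, which does not use the positive category, so nothing below changes it.

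**2. Inputs for the category.** The documents give no rate of ECG positivity, no rate of clinical positivity during exercise, and no within-woman correlation. All rates below are assumptions, chosen to show direction and range:

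- ECG-positive at both tests 10%, early only 20%, late only 2%, neither 68%. That is 30% early against 12% late, an 18-point difference.
- *c* is the chance that a test is clinically positive, independent of ST status.

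**3. Symptoms equal in both phases.** Pooled positivity is 1 − (1 − p)(1 − c), where p is ECG positivity. The pooled difference is therefore (1 − c) × 18 points.

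Discordant-pair probabilities:

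- If the same women are clinically positive at both tests: early only (1 − c) × 0.20, late only (1 − c) × 0.02.
- If clinical positivity is independent between tests: add 0.68 × c × (1 − c) to each. At c = 0.2 this adds 0.109, giving 0.269 and 0.125.

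Power of the exact two-sided McNemar test at 34 pairs, summed over the binomial number of discordant pairs:

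| c | Pooled difference (points) | Power, same women both times | Power, independent |
|---|---|---|---|
| 0 (ECG only) | 18.0 | 0.50 | 0.50 |
| 0.05 | 17.1 | 0.46 | 0.36 |
| 0.1 | 16.2 | 0.42 | 0.28 |
| 0.2 | 14.4 | 0.33 | 0.18 |
| 0.3 | 12.6 | 0.24 | 0.14 |
| 0.5 | 9.0 | 0.09 | 0.08 |

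With a larger assumed effect (both 10%, early only 30%, late only 5%; 25 points), ECG-only power is 0.65. At c = 0.2 the difference is 0.8 × 25 = 20 points, and power is 0.51 (same women) or 0.33 (independent).

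**4. Symptoms that differ by phase.** Using the 30% and 12% ECG rates:

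- Clinical positivity 30% early, 10% late: (1 − 0.70 × 0.70) − (1 − 0.88 × 0.90) = 0.510 − 0.208 = +30.2 points.
- Clinical positivity 10% early, 30% late: (1 − 0.70 × 0.90) − (1 − 0.88 × 0.70) = 0.370 − 0.384 = −1.4 points.

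The same 18-point ECG difference can therefore appear much larger, or vanish with a change of sign.

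**The case against.** **The category is not an endpoint.** The primary endpoint is the continuous ST/HR index, and ST/HR slope and maximum ST depression are listed secondaries. The ST phenomenon is measured three ways that chest pain does not enter by definition. This stands, and it limits the consequence to one unlisted comparison. A reader might infer that the study's ST conclusions or its sample size are compromised; the documents do not support that. The category is not idle, however, because the objective and hypothesis are worded in terms of ETT results, the phrase that section 2 uses for these categories.

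**Merging is inferred.** The protocol labels the two kinds of positive test differently and never says outright that they are combined for analysis. This also stands. It would go too far to say that the plan commits to pooling. What can be said is that the three-level sentence reads that way and that no separate analysis is specified.

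**Symptoms are part of a clinical test result.** The stated purpose refers to false positive test results, not to ST positivity alone, so a symptom-positive test falls within that wording. That is a reason to keep showing the pooled category, not a reason to leave out ECG positivity.

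**The power figures rest on invented rates and on a test the SAP does not name.** Both parts are true. Enrolment for chest pain does not fix how often pain occurs on the treadmill. If it is rare, or recurs in the same women, the loss is small: 0.50 to 0.46 at c = 0.05. Separation also does not make the comparison well powered, since ECG-only power is itself about 0.50 in the main example.

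**Conclusion.** The point holds in a limited form. The protocol most naturally describes one positive level containing both ECG-positive and clinically positive tests, and neither document plans to analyse them apart. Because the women were enrolled for chest pain and know their phase, that level can dilute or distort the phase contrast in ECG positivity.

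A reader might infer that pooling must dilute any phase effect. That holds only if clinical positivity does not depend on phase. Protocol section 1 says that menstrual phase affects physical working capacity and that oestrogen is vasodilatory, so symptoms or haemodynamic response could themselves shift with phase. The direction is therefore not fixed.

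The size is unknown. The illustrated range runs from a slight loss at low symptom rates to a halved difference at c = 0.5, or a distortion in either direction if symptoms differ by phase. All of it assumes rates that the documents do not give, with clinical positivity independent of ST status. It is worth correcting because the study frames its problem as false positive stress ECGs and the correction is cheap. It does not threaten the primary analysis.

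**What to change.** In the SAP:

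1. Compare ECG-positive (yes/no) between the early and late follicular phases with a paired test (McNemar), since each woman is tested twice and the chi-square test named for categorical data does not use the pairing.
2. Report clinically positive tests by phase in a separate row.
3. Show the pooled three-level category alongside.
4. State whether the category is a secondary or a descriptive outcome.

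Both definitions are already in the protocol and both components are already judged at every test, so no new data are needed. The cost is a short SAP addition, one more table row and one more secondary comparison. With 34 pairs that comparison will probably have low power, so it should be presented with the paired difference and its confidence interval and not only a p-value.
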